5.4. Prior and Concomitant Medication

All medications taken up to 30 days prior to the screening visit through the end of study (30 days after the last dose of study drug), need to be recorded in the source documents and on the eCRF. At each study visit, the study center will record any and all concomitant medications taken by the subject since the last visit or during the visit (as applicable). All concomitant medications (prescription, peri-procedural medications, over-the-counter medications, including vaccines, vitamins, herbal, dietary supplements, and minerals) must be recorded in the concomitant therapy section of the eCRF.

Effective current therapies should not be discontinued for the sole purpose of participating in this study. Subjects may receive medication as supportive care or to treat AEs as deemed necessary by the Investigator or the subject's physician. Should subjects have a need to initiate treatment with any excluded concomitant medication, the Study Medical Monitor should be consulted prior to initiation of the new medication. In instances where an excluded medication is initiated prior to discussion with the Sponsor, the Investigator should notify Gilead as soon as he/she is aware of the use of the excluded medication.

5.4.1. Allowed Concomitant Medication

The allowed concomitant medication(s) for CD must be maintained at a stable dose for the noted time without dose alteration or discontinuation. Subjects should not initiate new induction therapy prior to the screening visit. If a new therapy has been recently initiated, the full induction course should be completed prior to screening consideration.

The allowed medications for CD are as follows:

- Oral 5-ASA compounds provided the dose prescribed has been stable for at least 4 weeks prior to randomization; dose must be stable for the first 10 weeks after randomization
- Azathioprine, 6-MP, or MTX provided the dose prescribed has been stable for 4 weeks prior to randomization; dose must be stable for the first 10 weeks after randomization
- Oral corticosteroid therapy (prednisone prescribed at a stable dose of \leq 20 mg/day or budesonide prescribed at a stable dose of \leq 6 mg/day) provided the dose prescribed has been stable for 4 weeks prior to randomization; dose must be stable for the first 10 weeks after randomization.
- Antidiarrheals for chronic diarrhea are allowed throughout the study as necessary for control of chronic diarrhea; stable doses are encouraged.
- Occasional use of non-steroidal anti-inflammatory drugs (NSAIDs) for transient symptoms is permitted; daily use of aspirin up to 162.5 mg for the purpose of cardiovascular prophylaxis is permitted.
- Antibiotics for the treatment of perianal fistulizing CD (eg, metronidazole, ciprofloxacin) provided the dose prescribed has been stable for the 2 weeks prior to randomization. Dose must remain stable for the first 10 weeks after randomization. Subjects who are on cyclic therapy must continue their standard low-dose regimen without change for the first 10 weeks after randomization
- Vedolizumab therapy (300 mg IV) for the treatment of concurrent luminal disease activity provided the dose has been stable for 14 weeks prior to randomization; subjects must remain on vedolizumab for the duration of their participation in the study. Subjects on concurrent vedolizumab therapy must not be taking concurrent azathioprine or 6-MP or methotrexate.

5.4.2. Prohibited Concomitant Medication

The prohibited medications are as follows:

Table 5-1. Prohibited Concomitant Medication

Drug Class	Agents Disallowed	Prohibited Period
Strong P-gp Inducers^a		
Anticonvulsants	Phenobarbital, phenytoin, carbamazepine,	30 days prior to screening through the end of the study
Antimycobacterials	Rifabutin, rifapentine, rifampin	
Herbal/Natural Supplements	St. John's wort, danshen (salvia miltorrhiza)	
Prohibited IBD Medication		
Corticosteroids	Dose equivalent to > 20 mg/day of prednisone	30 days prior to screening through the end of the study
TNF α antagonist	Infliximab, adalimumab, golimumab, certolizumab, or biosimilar agent	8 weeks prior to screening through the end of the study
Integrin antagonist	Natalizumab	8 weeks prior to screening through the end of the study
Interleukin antagonist	Ustekinumab	12 weeks prior to Screening through the end of the study
JAK inhibitors	any JAK inhibitors, including but not limited to tofacitinib, baricitinib, and upadacitinib	Any time before and through the end of the study
Other (non-biologic)	Cyclosporine, thalidomide, tacrolimus, leflunomide, and any investigational agent	30 days prior to screening through the end of the study
Investigational biologics	Any investigational biologic agent	8 weeks prior to screening through the end of the study (or at least 5 half-lives)
Lymphocyte-depleting therapies	Alemtuzumab, cyclophosphamide, total lymphoid irradiation, rituximab, and any other lymphocyte depleting therapy	Any time before and through the end of the study
Other Prohibited Medication		
Chronic Nonsteroidal Anti-inflammatory Drugs (NSAIDs) ^b	Aspirin, ibuprofen, naproxen, diclofenac, indomethacin, COX-2 inhibitors	From screening through the end of the study
Other biologics ^c	Antibody based or other systemic biologics, eg, denosumab, trastuzumab	Requires medical monitor consultation

a May decrease study drug exposure and are excluded to avoid potential reduction in study drug activity. PK results indicate that filgotinib is a P-gp substrate, as a single dose of 200 mg itraconazole (a potent P-gp inhibitor) increased filgotinib C_{max} by 64% and AUC_{inf} by 45% and had no effect on the major, active metabolite GS-829845.

b Occasional use of NSAIDs for transient symptoms and daily use of aspirin up to 162.5 mg for the purpose of cardiovascular prophylaxis are permitted.

c Other biologics may be allowed with the approval of the medical monitor.

5.5. Corticosteroid Tapering

Starting at Week 10, subjects who are on concomitant steroids must begin tapering steroid therapy. The dose should be reduced at a rate starting at 2.5 mg per week up to 5 mg per week (or equivalent taper if not prednisone) until the subject is no longer on steroids. Subjects who are on budesonide should have their daily dose reduced by 3 mg every 3 weeks until they are completely off steroids. For subjects undergoing taper, steroids may be increased or restarted at doses up to and including their baseline dose if return of symptoms is apparent. These subjects will not be considered treatment failures. Subjects who need to restart or increase steroid treatment at a dose that exceeds their baseline dose of steroids (dose may not exceed 20 mg/day prednisone [or equivalent] or budesonide 6 mg/day) will be considered treatment failures for all clinical endpoints but will be permitted to remain in the study and continue to receive study drug.

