### 5.2. Baseline Disease Characteristics

Stratification factors (listed in Section 3.3) and other baseline disease characteristics listed below will be summarized for the Safety Analysis Set by the same method as demographic tables, using descriptive statistics for continuous variables and using number and percentage of subjects for categorical variables.

- Duration of perianal fistulizing CD (years) from date of diagnosis to first dosing date of study drug
- Duration of perianal fistulizing CD group (< 1 year,  $\geq$  1 to  $<$  3 years,  $\geq$  3 to  $<$  7 years,  $\geq$  7 years)

- Location of CD: ileal, colonic, ileocolonic and isolated upper disease
- [Redacted]
- Active Luminal Disease (CDAI  $\geq 150$ )
- Moderately Active Luminal Disease (CDAI  $\geq 220$ )
- Baseline Proctitis SES-CD score (sum of size of ulcers and ulcerated surface for the rectum and anal canal segments)
- Baseline Anal Canal SES-CD score (sum of size of ulcers and ulcerated surface for the anal canal segment)
- Presence of Moderately to Severely Active Proctitis (yes, no)

- Number of Draining Perianal Fistula at Baseline
- Anatomy of draining perianal fistulae at screening determined by MRI (simple vs complex)
- History of complications of perianal CD
  - Anal stenosis (yes, no)
  - Perirectal / perianal abscess (yes, no)
- Perianal Fistulizing CD treatment history
  - Prior use of antibiotics (yes, no)
  - Prior use of immunomodulators (yes, no)
  - Prior use of TNF $\alpha$  antagonist as listed in [Appendix 2](#) (yes, no); and for subjects with prior use:
    - Number of TNF $\alpha$  antagonists used
      - 1
      - 2
      - $\geq 3$

- Worst outcome of prior use of TNF $\alpha$  antagonist
  - Treatment failure
  - Intolerance, including both allergic and non-allergic intolerance
  - Other
- Other CD treatment history
  - Prior use of systemic corticosteroids (yes, no)
  - Number of prior exposure to biologic agent for CD as listed in [Appendix 3](#) (0, 1, 2,  $\geq 3$ )
  - Prior use of vedolizumab (yes, no); and for subjects with prior use:
    - Worst outcome of prior use of vedolizumab
      - Treatment failure
      - Intolerance, including both allergic and non-allergic intolerance
      - Other
    - Prior use of ustekinumab (yes, no) and for subjects with prior use:
      - Worst outcome of prior use of ustekinumab
        - Treatment failure
        - Intolerance, including both allergic and non-allergic intolerance
        - Other

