## 6. EFFICACY ANALYSES

### 6.1. General Considerations

The efficacy analysis will be conducted on the FAS, defined in Section 3.1.2, unless otherwise specified. No formal hypothesis testing will be performed.

The definitions of selected efficacy endpoints are provided in [Table 6-1](#). [Appendix 10](#) and [Appendix 11](#) include detailed definition of study treatment failure and the corresponding data handling rules for efficacy analysis.

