**Table 6-1. Definitions of Selected Efficacy Endpoints**

Type	Endpoint	Definition
Primary	Combined fistula response at Week 24	Reduction of $\geq 1$ from baseline in the number of draining external perianal fistula openings that were present at baseline, and absence of fluid collections $> 1\text{cm}$ on MRI pelvis at Week 24, among subjects with at least 1 draining external perianal fistula opening at baseline
Secondary	Combined fistula remission at Week 24	Perianal fistula closure of all external openings that were draining at baseline, and absence of fluid collections $> 1\text{cm}$ on MRI pelvis at Week 24, among subjects with at least 1 draining external perianal fistula opening at baseline
Secondary	Time to clinical fistula response	The time interval in days from date of first dosing of study drug to the first observation (during scheduled or unscheduled clinical visits) when $\geq 1$ of the draining external perianal fistula openings that were present at baseline achieves perianal fistula closure, among subjects with at least 1 draining external perianal fistula opening at baseline. Subjects not known to have a clinical fistula response will have their clinical fistula response time censored at the last time that lack of clinical fistula response was documented.

Type	Endpoint	Definition
Secondary	Time to clinical fistula remission	The time interval in days from date of first dosing of study drug to the first observation (during scheduled or unscheduled clinical visits) of perianal fistula closure of all external openings that were draining at baseline, among subjects with at least 1 draining external perianal fistula opening at baseline. Subjects not known to have a clinical fistula remission will have their clinical fistula remission time censored at the last time that lack of clinical fistula remission was documented.
Secondary	Proctitis remission at Week 24, in subjects that had moderately to severely active proctitis at baseline	A Proctitis SES-CD Score (sum of ulcer size and ulcerated surface SES-CD endoscopy subscores for the rectum and anal canal) of 0 assessed by centrally read flexible sigmoidoscopy at Week 24, in subjects that had moderately to severely active proctitis at baseline
		CCI
		CCI

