### 6.3.2. Analysis of the Secondary Efficacy Endpoints

For binary endpoints, the same statistical analysis method for analyzing the primary efficacy endpoint will be utilized.

If the proctitis SES-CD score is missing at Week 24, no imputation will be done and the subject will be considered a non-responder when deriving the proportion of subjects achieving proctitis remission at Week 24.

For time-to-event secondary efficacy endpoints, the summary statistics (eg, median, Q1, Q3) from the Kaplan-Meier method will be provided for each treatment group. Plot of Kaplan-Meier curves will also be provided. The Cox proportional hazards model will be used to estimate the hazard ratio with the corresponding 90% CI. Subjects not known to have a clinical fistula response (or remission) will have their clinical fistula response (or remission) time censored at the last perianal fistula assessment date.

No formal hypothesis testing will be performed.

CCI

CCI

[figure not shown]
CCI

CCI

CCI

CCI

CCI

CCI

The figure consists of a 10x10 grid of black bars on a white background. The bars are arranged in a pattern where most are horizontal, with some vertical and diagonal variations. The bars are of varying lengths, creating a stepped effect. The grid is bounded by a thick black border.

CCI

CCI

■

■

■

■

■

■

■

■

■

■

■

■

■

■

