### **I. Potentially effective corticosteroid use**

Potentially effective corticosteroids, for the purpose of this SAP, are corticosteroids that may impact the disease under study. **Potentially effective corticosteroids** include the following corticosteroids when administered for the indication of CD:

- 1) Commencement of:

Any steroid administered intramuscularly (IM), intravenously (IV), orally (PO), or rectally (PR) at any dose for 7 or more continuous days

- This rule applies regardless if a change in drug, dose, or route (from IM to IV to PO or PR or vice versa) occurs within the seven continuous days; and it includes oral steroids with intended local actions (eg, budesonide)

- 2) Escalation of concomitant steroid dose above the baseline dose for 7 or more continuous days. The baseline steroid dose is defined as the dose at Day 1 of the study. Prednisone equivalent dose will be used to determine escalation of concomitant systemic steroid dose even if there is a change in drug or route. For steroids with predominant local effect (eg, budesonide or any rectally administered steroid), this rule will apply to scenarios where the post-baseline dose is above the baseline dose via the same drug and the same route for 7 or more continuous days.

Potentially effective steroid use only includes use of steroids administered via routes that are IM, PO, IV, or PR. The below steroids will **not** be considered potentially effective steroids regardless of indication for use:

- A) ocular steroids (ie, eye drops)
- B) topical steroids (eg, cutaneously applied solely to the skin, or topically applied to the nasal mucosa)
- C) inhaled steroids (eg, inhalational fluticasone for asthma)
- D) intra-articular steroids (steroids administered directly into a joint)
- E) neuraxial steroids (steroids administered into the epidural or spinal space)

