## **Appendix 11. Study Treatment Failure Rules for Perianal Fistulizing CD Activity Related Efficacy Endpoints**

Study treatment failure rules described in this appendix apply to treatment failure that occurs during the course of the study, and will be applied to all the following efficacy endpoints related to perianal fistulizing CD activity:

- Proportion of subjects establishing combined fistula response at Week 24
- Proportion of subjects establishing combined fistula remission at Week 24
- Time to clinical fistula response
- Time to clinical fistula remission

All related efficacy data will be censored (set to missing) after treatment failure criteria are met, regardless of the observed data. Subjects who do not have sufficient measurements after censoring to determine the dichotomized endpoint(s) will be considered non-responder for corresponding endpoint (s). Study treatment failure rules override other data handling rules.

Subjects who have any of the following events will be considered a study treatment failure after the earliest event through the end of the study, regardless of the actual efficacy data collected.

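### Protocol 5.5 makes above-baseline steroid use a failure for every clinical endpoint, but SAP Appendix 11 has no steroid criterion for the two time-to-clinical-fistula endpoints, and no visible text reconciles them

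*Protocol*

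**What the plan says.** - **Protocol 5.5.** Steroid tapering starts at Week 10. Going back up to, but not beyond, the baseline dose is not a failure. Subjects who restart or increase above baseline, within the stated cap, "will be considered treatment failures for all clinical endpoints but will be permitted to remain in the study and continue to receive study drug". The section gives no minimum duration, and the protocol does not define *clinical endpoints*.
- **SAP 6.1.** Appendices 10 and 11 "include detailed definition of study treatment failure and the corresponding data handling rules for efficacy analysis".
- **SAP Appendix 11.** Its rules "will be applied to all the following efficacy endpoints related to perianal fistulizing CD activity". The four endpoints are combined fistula response and remission at Week 24, and time to clinical fistula response and remission. The criteria run from I to III without a visible gap: antibiotics, immunomodulators, biologics. The consequence is: "All related efficacy data will be censored (set to missing) after treatment failure criteria are met, regardless of the observed data".
- **SAP Appendix 10.** This covers endpoints related to luminal disease, of which only proctitis remission is legible. It holds the only visible steroid criterion, including "Escalation of concomitant steroid dose above the baseline dose for 7 or more continuous days".
- **SAP Table 6-1 and 6.3.2.** The event for remission is "the first observation (during scheduled or unscheduled clinical visits) of perianal fistula closure of all external openings that were draining at baseline". The response event needs at least one such opening to close. Neither carries a condition on steroid use. Subjects without an event have their "time censored at the last perianal fistula assessment date".

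**The concern.** A subject who goes above the baseline steroid dose stays on study drug and keeps having perianal assessments, so a first closure can be recorded afterwards. The protocol, read plainly, calls that subject a failure for endpoints whose own names contain the word *clinical*. The SAP, followed as written, records an event.

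The study is descriptive, so the Kaplan-Meier summaries and the hazard ratio with its 90% interval are what these two endpoints deliver. At stake is whether those estimates describe the endpoint that the protocol defines.

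**Working it through.** **Passages side by side**

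| Question | Protocol 5.5 | SAP as written |
|---|---|---|
| What steroid use is a failure? | Any dose above baseline; no minimum duration | Appendix 10 only: escalation above baseline (or commencement) lasting at least 7 continuous days |
| For which endpoints? | All clinical endpoints (undefined) | Luminal-related endpoints; none of the four fistula endpoints |
| Fistula closure first seen afterwards | Subject is a failure | Event on that date (Table 6-1) |

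**One subject traced through.** Suppose the dose goes above baseline between the Week 10 and Week 14 visits, and all baseline-draining openings are first closed at Week 18. No criterion in Appendix 11 is met, so the Week 18 record is not set to missing, and Table 6-1 gives a remission event at Day 127. Section 6.3.2 censors only subjects without an event. Non-responder imputation (SAP 6.1) covers binary endpoints with insufficient measurements, so it does not intervene.

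**Who can be affected.** The subject must meet all of these conditions:
1. takes steroids at baseline below the cap in Protocol 5.5, since at the cap there is no room above baseline;
2. goes above baseline after tapering starts at Week 10;
3. does not leave under Protocol 3.4 as a Week 10 non-responder or for later worsening;
4. has a first closure only after the increase. An earlier closure stays an event, because Appendix 11 removes only later data.

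The assessments at issue are Weeks 14, 18 and 24, and any early-termination, post-treatment or unscheduled perianal assessment after the increase.

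**Size.** The documents give no steroid or closure rates, and the plan states no figure on this point. Arm sizes are 30, 30 and 15 (Protocol 8.8), so one subject is 1/15 = 6.7 points on placebo or 1/30 = 3.3 points on a filgotinib dose.

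**Illustration on assumed data, not trial data.** Filgotinib has 15 events in 30: one at Day 15, two at Day 29, three at Day 43, four at Day 71, two at Day 99, two at Day 127, one at Day 169. Placebo has 5 events in 15: one each at Days 43, 71, 99, 127, 169. All others are censored at Day 169. The Cox model uses Efron ties and is unstratified, as in SAP 6.3.2. One Day 127 event is recoded.

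| Case | Hazard ratio (90% CI) | Week 24 Kaplan-Meier, recoded arm |
|---|---|---|
| As the SAP counts it | 1.83 (0.78-4.27) | placebo 5/15 = 33.3%; filgotinib 15/30 = 50.0% |
| Placebo subject censored at Day 99 | 2.26 (0.89-5.69) | 1 - (12/15)(10/11) = 27.3% |
| Placebo subject a non-event to Day 169 | 2.30 (0.91-5.81) | 4/15 = 26.7% |
| Filgotinib subject censored at Day 99 | 1.70 (0.72-4.02) | 1 - (18/30)(16/17)(15/16) = 47.1% |
| Filgotinib subject a non-event to Day 169 | 1.68 (0.71-3.96) | 14/30 = 46.7% |

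Across assumed counts of 12 to 18 events in 30 and 3 to 6 in 15, one placebo recode multiplies the hazard ratio by 1.19 to 1.52, and one filgotinib recode by 0.90 to 0.95. The direction depends on the arm in which the subject falls.

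**The case against.** The strongest reply is that the omission is deliberate.

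- Inclusion criterion 8 (Protocol 4.2) names antibiotics, immunomodulators and TNF antagonists as the qualifying failed therapies, with no steroids. Appendix 11 uses the same three classes.
- SAP 5.2 lists those three under perianal fistulizing treatment history, and systemic corticosteroids under other Crohn's disease treatment.
- Appendix 11 is not Appendix 10 with one item lost. It adds antibiotics, points to the TNF-only list in Appendix 2 instead of the broader list in Appendix 3, and widens the immunomodulator indication. That looks like a considered split by disease domain.

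The meaning of *clinical* is also less settled than the endpoint names suggest. The protocol's definition of terms uses it for the drainage-only fistula endpoints, but Protocol 1.1 and 1.2.3.1 use *clinical remission* for symptom-score and CDAI outcomes.

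Finally, parts of SAP 6.1, the text after 6.3.2 up to Section 7, and several Appendix 10 endpoints are redacted and could hold an explanation. SAP 7.7, which reports no deviations, speaks only of safety.

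All of this stands as an account of why steroids are absent from Appendix 11, and it bars calling the omission an outright mistake. It does not reconcile the appendix with a protocol sentence that says *all*. A luminal-only reading of that sentence is possible, but it would have to exclude two endpoints named clinical.

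A reader might also infer that the primary endpoint is misclassified. The documents do not support that. Combined fistula response adds an MRI component, and whether it is a clinical endpoint in the sense of Protocol 5.5 is not stated.

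**Conclusion.** The two passages conflict, and this should be fixed before unblinding. As written, the SAP can count a closure that the protocol, on its plain reading, excludes from time to clinical fistula response and time to clinical fistula remission.

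The number of subjects is unknown and may be zero; the direction is unknown; and no decision rests on it, because no hypothesis test is planned. The per-subject weights (6.7 and 3.3 points) follow from the planned arm sizes. The hazard-ratio shifts rest wholly on assumed counts and on at least one affected subject existing.

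The conclusion assumes that *all clinical endpoints* includes endpoints so named, and that no redacted text addresses the point. It does not extend to a finding that the SAP authors erred or that the combined endpoints are affected. It concerns endpoint classification only and takes no view on steroid management.

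**What to change.** Reconcile Protocol 5.5 and SAP Appendix 11 before unblinding:

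1. **Time to clinical fistula response and remission.** Apply the Protocol 5.5 criterion in Appendix 11, so that a closure first seen after the steroid event is not counted. Under the appendix's set-to-missing rule, censor at the last assessment before that event, and say so in 6.3.2. Because this censoring may be informative, add a sensitivity analysis that keeps the subject as a non-event to Week 24.
2. **If the split by disease domain is intended,** record it as a departure from Protocol 5.5 and report the protocol-consistent result as a sensitivity analysis.
3. **Combined endpoints.** State whether *clinical endpoints* includes them. Apply the same rule, as non-response at Week 24, only if it does.
4. **Do not copy Appendix 10 unchanged.** Its 7-continuous-day condition has no counterpart in Protocol 5.5. Its commencement item has no baseline-dose threshold, whereas Protocol 5.5 exempts a restart at or below baseline. These must be reconciled.

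The cost is SAP wording and one extra run of two analyses. Concomitant medications are already recorded at each visit (Protocol 5.4). If the SAP is already final, its Section 1 provides for documenting changes in the study report. The downside is slightly fewer events and possibly informative censoring.
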